2.5.2.2 Adverse Events (AEs)

The following treatment-emergent AE summaries will be provided by overall and by treatment group for the Safety Set 1 (SAF-1), presented by dose and cumulative duration of exposure:

- Overview of all TEAEs: Number of participants with at least one (Any AE, Any SAE, Any AE related to study drug, Any AE leading to discontinuation of study treatment, Deaths etc.)
- TEAEs by primary system organ class and preferred term,
- TEAEs by primary Standardized MedDRA Query (SMQ) and preferred term,
- TEAEs by primary system organ class, preferred term and maximum severity,
- TESAEs by primary system organ class and preferred term,
- TEAEs leading to permanent discontinuation of study-drug by primary system organ class and preferred term,
- Treatment Emergent Adverse events of special interest (AESI),
- Study treatment-related adverse events by primary system organ class and preferred term,
- Deaths by primary system organ class and preferred term including listing of deaths,

If a participant reported more than one AE with the same preferred term, the AE with the greatest severity will be presented. If a participant reported more than one AE within the same primary system organ class, the participant will be counted only once with the greatest severity at the system organ class level, where applicable.

Separate summaries will be provided for study treatment-related adverse events, death, serious adverse events, and other significant adverse events leading to discontinuation.

2.5.2.3 Adverse events of special interest / grouping of AEs

AEs of special interest (AESI) are defined in the latest version of the compound electronic Case Retrieval Strategy (eCRS). The classification reflects the safety topics of interest identified in the current version of the QGE031 Development Safety Profiling Plan and may be updated based on review of accumulating data. The number and percentage of participants with treatment emergent AEs of special interest will be summarized by risk category, PT and treatment. The search criteria in the latest eCRS corresponding the MedDRA version at the database lock will be used and reported in the CSR:

- Hypersensitivity reactions (including anaphylaxis)
- Cardiovascular and Cerebrovascular (CCV) events

- Neoplastic conditions
- Injection site reactions
- Serum Sickness
- Eosinophilic Conditions / Churg-Strauss Syndrome
- Parasitic (Helminthic) infections
- Thrombocytopenia

Adjudicated AEs

From the AESIs listed above, the following AEs will be adjudicated by the independent committee. The adjudicated events will be listed, and a summary table may be provided following the adjudication.

- Anaphylaxis
- Cardiovascular and Cerebrovascular (CCV) events
- Neoplastic conditions

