- NOTE: The Investigator is able to check the level of desensitization by SPT at Week 76 (scheduled time point) and can decide to conduct an ad hoc OL-OFC in case of positive (or shift from prior assessment) SPT. The same (SPT followed by OL-OFC) is allowed in case of a suspected allergic event during the off-treatment period. The results of the ad hoc OL-OFC may lead to the resumption of study treatment (at the same dose as in the core study) after at least 24 h from completion of the OL-OFC, and treatment will continue until the EoT of the extension study (Week 156).
- For participants who have received the study treatment in the first year until Week 52 (i.e., participants who did not have OL-OFC at Screening/Day 1):
 - 1. If the participants meet the definition of MR by OL-OFC at Week 52, the interruption of study treatment (off-treatment) will be initiated.
 - If the participants still meet the definition of MR by OL-OFC after 16 weeks of study treatment interruption (at Week 68), the interruption (off-treatment) period will be extended up to Week 104.
 - If the participants are no longer MR by OL-OFC after 16 weeks of study treatment interruption (at Week 68), the study treatment will be re-started (same dose as in previous year) after at least 24 h from completion of the OL-OFC. If the participants become MR again at a later timepoint, no interruption of treatment is commenced. The study treatment will continue until the EoT of the extension study (Week 156).
- NOTE: The investigator is able to check the level of desensitization by SPT at an unscheduled time point prior to Week 104, and the results of the ad hoc OL-OFC may lead to the resumption of study treatment (same dose as taken previously) after at least 24 h from completion of the OL-OFC and treatment will continue until the EoT of the extension study (Week 156).

• If the participants do not meet the definition of MR by OL-OFC at Week 52, the study treatment will be continued (same dose as in the previous year) until Week 104.

Third year:

- For participants who have been off-treatment in the second year until Week 104:
 - 1. If the participants meet the definition of MR by OL-OFC at Week 104, the off-treatment period will continue up to Week 156.

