2.5 Analysis supporting primary objective(s)

2.5.1 Primary safety endpoint(s)

The primary objective of the study is to assess the long-term safety and tolerability of ligelizumab in participants with food allergy for an additional three-year period after a core study.

Page 15 of 28 Study No. CQGE031G12303B

Primary endpoints are overall incidence and exposure-adjusted occurrence rates (EAOR) of treatment-emergent adverse events (TEAEs) and serious adverse events (TESAEs), however, due to early termination of the study, EAOR will not be calculated.

TEAEs are defined as events that either:

- 1) Where an AE either started after the first dose of extension study treatment and within 16 weeks after the last administered study treatment dose or
- 2) began prior to the first dose of study treatment but increased in severity (based on preferred term) within 16 weeks after the last study treatment.

All participants enrolled into the extension study, regardless of which preceding studies they came from, will be included in the safety analysis. All listings and tables will be presented by treatment dose. All data will be included in the analysis, regardless of rescue medication use.

This analysis will be based on SAF-1.

For all adverse events tables the events that the investigator classified as reactions associated to the Oral Food Challenge (OFC)or Skin Prick Test (SPT) will not be included in reporting of treatment-emergent adverse events (TEAEs).

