2.5.2 Statistical method of analysis

Summary statistics for primary endpoints overall incidence of treatment-emergent adverse events (TEAEs) and serious adverse events (TESAEs) will be provided as follows:

The number and percentages of participants with at least one event (incidence rates)

The crude incidence rate is defined as the percentage of participants with a specific adverse event divided by the total number of participants in each study group.

Due to expected differences in exposure and follow-up due to varied duration of study participation between participants, adverse event incidence rates will be provided as "exposure adjusted AE incidence rates" in addition to the crude incidence.

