2.5.2.1 Exposure-Adjusted Incidence rate and 95% confidence interval

The EAIR is defined as the number of participants with a specific event divided by the total exposure-time among the participants in the study group. That is, the EAIR is calculated as:

 $EAIR = n / \Sigma t_i$, where n is the number of participants having the i^{th} type event, and t_i is a participant's exposure time and defined as the shortest of the following:

- 1. Time to the first episode of the i^{th} type event (if the event occurs),
- 2. Time to the end of observation period, or
- 3. duration of study treatment plus the 16-week washout period (approximately corresponding to five half-lives) after last treatment dose

The total exposure time of all participants in a treatment group is Σ t_i . The EAIR is interpreted as the number of events occurring in a population per unit time. The exact Poisson 95% confidence interval for the EAIR will be provided as well, where an exact $100*(1-\alpha)\%$ confidence interval will be derived as follows (Garwood 1936, Sahai and Khurshid 1993):

- Lower confidence limit $L = \frac{0.5C_{\alpha/2,2n}}{\sum t_i}$ for n>0, 0 otherwise,
- Upper confidence limit $U = \frac{0.5C_{1-\alpha/2,2n+2}}{\sum t_i}$,

where $C_{\alpha,k}$ is the α th quantile of the Chi-square distribution with k degrees of freedom.

Whenever applicable, exposure adjusted incidence rates will be provided for the type as below:

- 1. TEAE and TESAE: Primary SOC level, PT level
- 2. Further safety analyses are defined in safety analyses (Section 2.8)

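### No exposure-adjusted rate is specified for AESI risk categories, so comparing doses at that level rests on crude percentages that depend on time at risk

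*SAP*

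**What the plan says.** SAP 2.5.2 gives the reason for exposure adjustment: "Due to expected differences in exposure and follow-up due to varied duration of study participation between participants". Adverse event incidence is therefore to be shown exposure-adjusted "in addition to the crude incidence".

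SAP 2.5.2.1 defines EAIR as participants with the event divided by person-time. Person-time stops at the first event of that type, at the end of observation, or at treatment duration plus 16 weeks, whichever is shortest. The levels listed are "TEAE and TESAE: Primary SOC level, PT level". Anything further is referred to SAP 2.8. The readable part of 2.8 covers registry tables, deaths, laboratory data and vital signs, and contains no EAIR.

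For AESIs, SAP 2.5.2.3 specifies: "The number and percentage of participants with treatment emergent AEs of special interest will be summarized by risk category, PT and treatment". Adjudicated anaphylaxis, cardio-cerebrovascular (CCV) and neoplastic events are to be listed, and a summary table is optional.

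SAP 2.5.2.2 includes AESIs among summaries for "Safety Set 1 (SAF-1), presented by dose and cumulative duration of exposure". Protocol 9.3.2 planned exposure-adjusted occurrence rates alongside incidence and named AESIs among the summaries. SAP 2.5.1 drops the occurrence rate because of early termination.

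**The concern.** An AESI risk category is a search-defined group of preferred terms, so neither the SOC rows nor the PT rows give its rate. At category level the SAP names only a percentage.

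That percentage depends on how long participants were at risk, and in this study time at risk can depend on response. Protocol 4.1.2.1 says of participants dosed through the first year: "If the participants meet the definition of MR by OL-OFC at Week 52, the interruption of study treatment (off-treatment) will be initiated". A treatment-emergent event must have "started after the first dose of extension study treatment and within 16 weeks after the last administered study treatment dose" (or be an earlier event that worsened in that window). A Maximum Responder (MR) who stops and does not restart therefore has a shorter window than a participant who continues.

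If MR stopping differs between 120 mg and 240 mg, crude category percentages can differ with no difference in the underlying rate. Safety is the primary objective, and the AESI table is where the sponsor's safety topics of interest will be compared by dose. Staggered entry and early termination give no reason of their own for a dose difference, but they leave the crude percentage without a defined period.

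**Working it through.** **The plan's own figures.** SAP 2.5.2.3 states none. The nearest are the Clopper-Pearson intervals for crude incidence in Protocol Table 9-1. All nine reproduce to two significant figures (for example, 2 of 200 gives 0.12% to 3.6%). The 1% and 3% rows at 550 need 5.5 and 16.5 events. The table concerns crude precision and does not bear on exposure.

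**Why PT rates do not give the category rate.** Take a participant with two PTs of one category, at times t1 < t2. The category EAIR needs one participant and person-time t1. The PT rows hold that participant twice, with person-time t1 in one row and t2 in the other. A participant with only one of the PTs contributes longer person-time to the other PT's row. Adding numerators double-counts, and no common denominator exists.

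**Inputs.**
- Windows, from SAP 2.5.1 and the Protocol schedule: last dose at Week 52 gives 52 + 16 = 68 weeks; Week 76 gives 76 + 16 = 92; Week 104 gives 104 + 16 = 120; Week 156 gives 156 + 16 = 172.
- Assumed, because the documents give no values: a constant rate L, equal at both doses; share f of dosed participants stopping as MR and not restarting, 30% at one dose and 10% at the other.

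**Formulas.** Risk over w weeks is P(w) = 1 − exp(−L·w/52). Crude incidence is (1 − f)·P(long) + f·P(short). Expected person-time to first event is P(w)/L, so EAIR equals L whatever the mix of windows.

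**Full three-year design, MRs stopping at Week 52.** At L = 0.05:
- P(68) = 1 − exp(−0.0654) = 6.33%; P(172) = 1 − exp(−0.1654) = 15.24%.
- f = 30%: 0.3 × 6.33 + 0.7 × 15.24 = 12.57%.
- f = 10%: 0.1 × 6.33 + 0.9 × 15.24 = 14.35%.

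| Case | L per year | Crude, f = 30% | Crude, f = 10% | EAIR, both |
|---|---|---|---|---|
| Dosing to Week 156, MR stop Week 52 | 0.01 | 2.67% | 3.06% | 0.01 |
| Same | 0.05 | 12.6% | 14.4% | 0.05 |
| Same | 0.10 | 23.4% | 26.6% | 0.10 |
| Same | 0.30 | 53.8% | 59.9% | 0.30 |
| Dosing to Week 156, MR stop Week 104 | 0.10 | 25.9% | 27.4% | 0.10 |
| All dosing ends Week 76, MR stop Week 52 | 0.10 | 15.0% | 15.8% | 0.10 |
| All dosing ends Week 52 | 0.10 | 12.3% | 12.3% | 0.10 |

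The last two rows represent early termination. If dosing ends at Week 52, MRs and others share the 68-week window and the effect vanishes.

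**What EAIR does not cure.** SAP 2.4.1 computes duration from first and last dose, so an interruption between them counts as exposure. Suppose MRs stop at Week 52, restart at Week 104 and are dosed to Week 156, with true rate 0.10 on drug and for 16 weeks after a dose, and zero in the remaining 36 weeks of the gap (68 to 104).
- Risk for a restarter: 1 − exp(−0.10 × 136/52) = 23.0%. Person-time: 1.226 + 0.877 × 36/52 + 0.877 × 1.226 = 2.909 years. Without interruption the figures are 28.16% and 2.816 years.
- f = 10%: 27.65% / 2.825 = 0.098. f = 30%: 26.62% / 2.844 = 0.094.

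Both understate 0.100, and the two doses still differ slightly.

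**The case against.** A reader might infer that AESIs receive no exposure adjustment at all. The documents do not support that. SAP 2.5.2 makes a general commitment to adjusted rates, EAIR is defined for any event type, AESI preferred terms receive PT-level EAIRs as TEAEs, and SAP 2.5.2.2 calls for presentation by cumulative exposure. What stands is narrower: the specific instructions do not carry the rate to the risk category. Presentation by cumulative exposure is a layout with no bands defined in the readable text, and it yields no rate.

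A reader might also infer that the dose with more Maximum Responders will look safer. That needs an MR imbalance among dosed participants, little restarting, and dosing past Week 52; the documents establish none of these. Protocol 4.1.2.1 rechallenges MRs at Weeks 68 and 104, and those who are no longer MR resume treatment. SAP 1 reports early termination, and SAP 2.6.1 maps some final challenges within 380 days to Week 52, which suggests that follow-up ended about then for some. From Protocol 9.3.2, MRs never dosed in the extension are outside SAF-1. With about 200 participants (SAP 3), split evenly by assumption, the standard error of 12.6% versus 14.4% is √(0.126 × 0.874/100 + 0.144 × 0.856/100) = 4.8 points, larger than the 1.8-point gap. The analysis is descriptive, with no test planned.

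Further, a constant rate may not suit hypersensitivity, since the Protocol concentrates observation on the first doses after a start or restart. Parts of the public SAP are not readable, including the analysis sets and perhaps some of 2.8, so an AESI rate could be specified there.

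**Conclusion.** In the readable text, no EAIR is specified at AESI risk-category level, and it cannot be recovered from the PT-level rates. Dose comparison by category therefore rests on crude percentages that depend on exposure, against the SAP's own reasoning in 2.5.2.

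The distortion is conditional and probably small here. Under the full design, with the assumed 30% versus 10% split and no restart, it is 1.8 points at 0.05 per participant-year. At 0.10 it is 0.8 points if dosing ends at Week 76 and nil if dosing ends near Week 52. These sizes rest on a constant and equal rate and on an MR split that the documents do not give.

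It would also go too far to call the AESI list the drug's known harms: Protocol 8.6.6 and SAP 2.5.2.3 present safety topics of interest. The change is worth making because it is cheap and uses a method already in the SAP. It reduces the dependence on exposure without removing it entirely.

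**What to change.** In the EAIR list of SAP 2.5.2.1, add a line for AESIs at risk-category and PT level, and one for adjudicated anaphylaxis, CCV and neoplastic events. Define the first event as the first of any PT in the category. Show the EAIR and its exact Poisson 95% interval beside n (%) in the 2.5.2.3 table.

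In the same section, state how off-treatment gaps longer than 16 weeks count in person-time, because the duration formula in SAP 2.4.1 now counts them as exposure.

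The cost is one extra table column and a small amount of programming, since the rate and interval are already specified for SOC and PT. The change concerns tabulation only and touches no treatment rule.

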Currently the standard of care for food allergy is limited to strict avoidance of the inciting food(s), rescue medication in case of unintentional exposure, and community wide interventions for schools (i.e., peanut free classrooms) and restaurants (i.e., ingredient alerts) (Jones, Burks 2017). Nevertheless, accidental exposures of food-sensitive individuals to the very antigen they are striving to avoid are frequent. For example, 58% of young children with clinical peanut hypersensitivity followed for up to 5 years experienced adverse reactions from accidental peanut exposure despite best efforts at allergen avoidance (Vander Leek et al 2000).

Recently, a peanut oral immunotherapy (OIT) (Vickery et al 2018) was approved by Food and Drug Administration (FDA) to mitigate allergic reactions during accidental exposure to peanuts

(Jan-2020) and by European Medicines Agency (EMA) for the treatment of peanut allergy (Dec-2020). However, this treatment is not fundamentally changing the unmet medical need in this space, as it is only targeting one allergen; it is indicated only for a subset of age groups and might not be suitable for all peanut allergic patients.

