In all completed studies to date, four cases have been positively adjudicated as anaphylaxis: three in asthma studies and one in a CSU study. Two out of four cases occurred after restart of ligelizumab. Investigators should therefore be alert to the occurrence of hypersensitivity events, including anaphylaxis, following the administration of ligelizumab and be familiar with the information and guidance provided.

IgE is an antibody that may have an adaptive role in immunity to parasitosis, particularly helminthic infections. Blocking the interaction of IgE and its receptors with ligelizumab may therefore alter immunologic responsiveness to parasites. For this reason, monitoring for the occurrence of infection and response to therapy is recommended for participants who receive ligelizumab and are at high risk of geohelminth infection. There is insufficient data to determine the length of monitoring required for geohelminth infections after stopping ligelizumab. However, it is expected that ligelizumab will not interfere with a polyclonal reaction triggered by exposure to parasites. The resulting increase of IgE production would decrease, through target-mediated disposition, the half-life of ligelizumab hence restoring normal IgE levels more rapidly.

In the most recent CSU Phase III program (Studies CQGE031C2302 and CQGE031C2303), a total of 2150 patients (including 93 adolescent patients) received ligelizumab 72 mg, 120 mg, omalizumab 300 mg and placebo. Ligelizumab was well-tolerated, consistent with previous studies.

Therefore, based on the cumulative data available across all clinical studies in different populations for ligelizumab, the current evidence suggests that ligelizumab is safe and well tolerated and thus appropriate for further development.

The non-clinical safety evaluation for ligelizumab supports the clinical treatment of children down to the age of 2 years. In a juvenile toxicity study that was conducted in 6-month-old cynomolgus monkeys there was no evidence to suggest that ligelizumab will have a different mode of action or will be cleared differently in pediatric versus adult participants. No new or unexpected safety signals were identified in the Study CQGE031C2201 (CSU dose-ranging) study in adults and in the Study CQGE031C2202 (CSU) in adolescents

Study treatments

Transition from the core study:

There are two groups of core study participants that will be enrolled in the extension study:

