8.6.1 Adverse events

An adverse event (AE) is any untoward medical occurrence (e.g., any unfavorable and unintended sign [including abnormal laboratory findings], symptom or disease) in a clinical investigation participant after providing written informed consent for participation in the study. Therefore, an AE may or may not be temporally or causally associated with the use of a medicinal (investigational) product.

The Investigator has the responsibility for managing the safety of individual participant and identifying adverse events.

Novartis qualified medical personnel will be readily available to advise on trial-related medical questions or problems.

The occurrence of adverse events must be sought by non-directive questioning of the participant at each visit during the study. Additionally, the investigator should proactively query the participants about the occurrence of specific adverse events suggestive of hypersensitivity reactions during and after the OFC, the administration of study drug, and in the event of accidental food ingestion. Adverse events also may be detected when they are volunteered by the participant during or between visits or through physical examination findings, laboratory test findings, or other assessments.

Adverse events must be recorded under the signs, symptoms, or diagnosis associated with them, accompanied by the following information (as far as possible) (if the event is serious refer to Section 8.6.2):

- 1. The severity grade
 - mild: usually transient in nature and generally not interfering with normal activities
 - moderate: sufficiently discomforting to interfere with normal activities
 - severe: prevents normal activities
- 2. Its relationship to the study treatment. If the event is due to lack of efficacy or progression of underlying illness (i.e., progression of the study indication) the assessment of causality will usually be 'Not suspected.' The rationale for this guidance is that the symptoms of a lack of efficacy or progression of underlying illness are not caused by the trial drug, they happen in spite of its administration and/or both lack of efficacy and progression of underlying disease can only be evaluated meaningfully by an analysis of cohorts, not on a single participant
- 3. Its duration (start and end dates or ongoing) and the outcome must be reported
- 4. Whether it constitutes a SAE (see Section 8.6.2 for definition of SAE) and which seriousness criteria have been met

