8.6.5 Disease-related events and/or disease-related outcomes not qualifying as AEs or SAEs

Not applicable.

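### The hypersensitivity AESI row pools reactions to accidental food with reactions to study drug, so its dose comparison mixes drug risk with protection against food

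*SAP*

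**What the plan says.** SAP 2.5.2.3 lists "Hypersensitivity reactions (including anaphylaxis" among the categories of special interest, retrieved by the search terms of the electronic Case Retrieval Strategy (eCRS). On layout it says: "The number and percentage of participants with treatment emergent AEs of special interest will be summarized by risk category, PT and treatment". No split by causality, timing or trigger is stated.

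Only one trigger-based exclusion appears. SAP 2.5.1 says that events the investigator classed as reactions to the "Oral Food Challenge (OFC)or Skin Prick Test (SPT) will not be included in reporting of treatment-emergent adverse events (TEAEs". Accidental ingestion is not named.

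Reactions to accidental ingestion are collected. Protocol 8.6.1 asks the investigator to query hypersensitivity "during and after the OFC, the administration of study drug, and in the event of accidental food ingestion". Protocol 8.6.5, headed "Disease-related events and/or disease-related outcomes not qualifying as AEs or SAEs", is marked not applicable, so no disease-related event is exempt from adverse event reporting.

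Anaphylaxis is also adjudicated. SAP 2.5.2.3 says: "The adjudicated events will be listed, and a summary table may be provided following the adjudication". Protocol 8.4.6.2 and 10.1.4.2 describe the assessment by clinical presentation and risk factors and leave the detail to a charter.

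**The concern.** In a food-allergic population the same terms describe a reaction to peanut and a reaction to the injection. By removing challenge and prick-test reactions, the SAP already accepts that allergen-triggered events blur the drug safety tables. It leaves the remaining allergen source in.

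The two sources can move in opposite directions with dose. If one dose protects better, its food reactions fall, and the row falls with them even if reactions to the injection rise. A reader comparing 120 mg with 240 mg on this row could draw the wrong conclusion about drug hypersensitivity.

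Protocol 2.3 calls anaphylaxis a class risk, says the risk on reintroduction after an interruption has not been characterised in this population, and reports that two of the four adjudicated cases followed a restart. Participants from the peanut core study enter after a washout.

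The treatment-emergent window adds to the mixing. Read literally, SAP 2.5.1 runs it from the first extension dose to 16 weeks after the last. Someone treated to Week 52, then off drug to Week 104 under Protocol 4.1.2.1 and then restarted stays inside the window throughout. Food reactions in that off-drug year therefore enter the same row.

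**Working it through.** **The plan's own figure.** Protocol 9.9.2 gives an exact 95% interval of 0.12% to 3.6% for a 1% rate in 200 participants. Clopper-Pearson for 2 of 200 gives 0.121% to 3.565%, so it reproduces. It is not in dispute, but it shows how little a row with a few events can say.

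**Inputs from the documents**
- Food: Protocol section 2 (Introduction) reports that "58% of young children with clinical peanut hypersensitivity followed for up to 5 years experienced adverse reactions from accidental peanut exposure".
- Drug: Protocol 2.3 states that "four cases have been positively adjudicated as anaphylaxis" in completed studies, and that about 2976 participants have been exposed, including in ongoing studies.
- Size: SAP section 3 expects about 200 participants.

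**Assumed inputs.** Constant hazard; one year of follow-up; 80% protection on 120 mg and 90% on 240 mg; a share *s* of food reactions that codes to the category. None of these is in the documents.

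**Food reactions**
- Hazard h = −ln(1 − 0.58)/5 = 0.1735 per year.
- Unprotected one-year risk = 1 − exp(−0.1735) = 15.9%, or 31.9 of 200.
- At 80% protection: 1 − exp(−0.1735 × 0.2) = 3.41%, or 6.8 of 200.
- At 90% protection: 1 − exp(−0.1735 × 0.1) = 1.72%, or 3.4 of 200.

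**Drug anaphylaxis.** 4/2976 = 0.134% (exact 95% interval 0.037% to 0.344%), or 0.27 of 200.

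**Dose illustration, s = 100%.** Pooled row = food risk + drug risk.

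| Drug anaphylaxis on 240 mg relative to 120 mg | 120 mg row | 240 mg row |
|---|---|---|
| equal | 3.41 + 0.13 = 3.54% | 1.72 + 0.13 = 1.85% |
| 5 times | 3.54% | 1.72 + 0.67 = 2.39% |
| 10 times | 3.54% | 1.72 + 1.34 = 3.06% |

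At five or ten times the drug risk, 240 mg still shows the lower row.

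**Sensitivity to s, with drug anaphylaxis five times higher on 240 mg.** Food risk = 1 − exp(−0.1735 × (1 − protection) × s).
- s = 50%: 1.72 + 0.13 = 1.85% against 0.86 + 0.67 = 1.54%. Still reversed.
- s = 25%: 0.86 + 0.13 = 1.00% against 0.43 + 0.67 = 1.10%. Not reversed.
- s = 10%: 0.35 + 0.13 = 0.48% against 0.17 + 0.67 = 0.85%. Not reversed.
- The rows are equal where the food difference equals 4 × 0.134% = 0.54%, which is at s of about 31%.

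**How far food outnumbers drug.** With s = 100%, the ratio of affected participants is 118:1 with no protection, 25:1 at 80% and 13:1 at 90%. With s = 10% it is 13:1, 2.6:1 and 1.3:1, and at 95% protection it falls to 0.6:1. The inputs allow almost any answer.

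**The case against.** The strongest reply is that drug reactions can be seen elsewhere and that nothing is tested.

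- The table has preferred-term rows as well as a category total, and injection site reactions have their own category.
- SAP 2.5.2.2 plans a table of treatment-related events. Protocol 8.6.1 says lack-of-efficacy events will usually be scored as not suspected, so that table does discriminate.
- Adjudicated anaphylaxis will be listed. With a fraction of a case expected, a listing may be enough.
- Protocol 7.1 stops treatment after a serious hypersensitivity event suspected to be drug-related, and discontinuations are tabulated.
- Protocol 9.3.2 plans separate safety tables for participants who restart.
- All analyses are descriptive, with no hypothesis test between doses.

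Most of this stands. A reader might infer that drug reactions would be swamped or invisible, but these outputs show otherwise. A reader might also take drug hypersensitivity to be the main known drug risk. Protocol 2.3 does not say so: the possible dose-related signal it names is injection site reactions.

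The reply does not remove the mixing in the row itself. The related-event table is by system organ class and preferred term, so drug hypersensitivity is not gathered into its category. The adjudicated summary is optional, and the visible text describes no classification by trigger. The visible SAP does not repeat the restart tables. Protocol 10.7.6 requires serious reactions around a challenge to be attributed to study treatment or challenge, but no matching attribution is stated for accidental food.

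**Conclusion.** The pooling follows from the text and needs no assumption: both sources enter one row, and nothing planned in that table separates them. The descriptive dose comparison in the row therefore mixes drug hypersensitivity with protection against food.

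The size is not known. The 3.54% against 2.39% shows that the row can mislead; it does not predict that it will. It rests on the assumed protection levels, a constant hazard, one year of follow-up and all food reactions coding to the category. Below a share of about 31%, the fivefold example no longer reverses.

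A headline such as food reactions outnumbering drug reactions by 13:1 to 118:1 is tempting, but the documents do not support it. The 58% is any reaction, in young children not on ligelizumab. The 4 in 2976 is adjudicated anaphylaxis only, in other indications, not annualised, and sets cases from completed studies over a denominator that includes ongoing ones.

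Three limits remain. The eCRS terms and adjudication charter are not among the documents, and parts of the SAP are redacted, so a split elsewhere cannot be excluded. The time on study after early termination is not stated, so interruptions followed by a restart may be few. This is a cheap improvement to reporting; it bears on how one safety table is read and on no test or planned conclusion.

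**What to change.** In SAP 2.5.2.3:

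1. Keep the overall hypersensitivity row, so that nothing is lost from safety detection.
2. Below it, by dose, split by investigator causality (suspected / not suspected) and by time since last injection. Add trigger (study drug, accidental food, other or unknown) where it is recorded.
3. Change the adjudicated-anaphylaxis summary from optional to definite, in the same layout.
4. Do not state that only suspected events, or only events within a fixed window such as the day of injection and the day after, count as drug hypersensitivity. The documents give no basis for such a window, and the rule would narrow detection.

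The cost is SAP wording and one restructured table. Onset dates and causality are collected under Protocol 8.6.1, dosing records are listed under SAP 2.4.1, and the example home diary in Protocol 10.9.10 asks for injection date and time. The documents show no dedicated trigger field for accidental ingestion, so that split may depend on narratives. Some events will have an uncertain trigger, and the cells will be small. No dose or clinical rule is affected.
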